This study will provide us with information about the diagnostic quality of the nutritional screening carried out in our environment compared with the GLIM criteria for malnutrition. In addition, by comparing the prevalence of sarcopenia and the phase angle in patients with positive or negative screening, we will be able to estimate the risk of muscle and cellular dysfunction in patients with the worst clinical prognosis.

Methods

Trial design:

Cross-sectional single-center study comparing the diagnostic quality of the CIPA instrument in the diagnosis of malnutrition or risk of presenting it in hospitalized patients vs GLIM and subsequent prospective follow-up of patients for up to six months.

The aims:

Primary endpoint:

- Determine the diagnostic quality of the CIPA tool, in inpatients with stays longer than three days, in the observation of risk of malnutrition compared to the gold standard GLIM as a diagnosis of malnutrition.

Secondary endpoints:

- Determine the positive and negative predictive values in comparison to the selected gold standard.
- Determine the degree of reliability, likelihood ratio and diagnostic odds ratio of the tool compared to the gold standard.

- Determine the point of greatest balance between sensitivity and specificity for each of the three variables that make up the diagnostic instrument for malnutrition.
- Determine the degree of Kappa concordance between both diagnostic criteria (CIPA vs. GLIM).
- Establish the cut-off point for the phase angle of the population studied by bioimpedanciometry for men and women, and determine prognostic values according to the optimal cut-off point.
- Evaluate prognostic variables (mortality, average stay, readmission rate) according to the two tools under study (CIPA vs. GLIM) at discharge, together with early readmissions, and mortality at six months of prospective follow-up.
- Evaluate whether CIPA positive subjects obtain worse muscle functionality results according to dynamometry than CIPA negative subjects.
- Determine if there is a relationship between positive CIPA and sarcopenia according to established EWGSOP2 diagnostic criteria.
- Determine if there is a relationship between positive subjects with sarcopenia vs negatives in relation to the six-month prognosis.

Inclusion criteria:

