For the cross-sectional study of the quality of diagnostic criteria between the CIPA instrument and the current gold standard GLIM, a study of sensitivity, specificity, positive and negative predictive values, as well as the likelihood and an estimator of a single value such as the diagnostic odds ratio. In addition, they will determine the best equilibrium points for the three items of the CIPA instrument according to the Youden model, determining in each case the area under the curve (AUC). Likewise, the concordance between both CIPA tests and the GLIM gold standard will be determined by the Kappa coefficient according to Cohen's model. All point estimates will be accompanied by 95% confidence intervals.

For the follow-up study with CIPA positive patients, an initial univariate study of the factors that could determine prognostic levels in the patients will be carried out. These analyzes will be parametric/non-parametric according to the homoscedasticity and normality of the data in each distribution, analyzed by the Kolmogorov-Smirnov test. Subsequently, for the variables with statistical significance or clinical relevance found in the univariate analysis, multivariate models will be carried out with the aim of knowing the one that best fits the data and determining the prognostic factors in the patients studied. The selection of the final model will be guided by the principle of parsimony. Collinearity will be evaluated by the main regression component of the explanatory variables. While

the different models will be compared by the likelihood ratio and the Wald test. The existence of confusion will be evaluated by clinical criteria with a significant change of 10% over the coefficient obtained according to the variables included in the model. The model will be validated by the Hosmer-Lemeshow calibration test and by the area under the curve (AUC) as a measure of discrimination.

Workplan:

This study will select patients with an expected hospital stay of more than three days, through probabilistic sampling to control possible biases in the selection of subjects. The selection will be made in the departments specified by physicians or personnel trained for this purpose, establishing whether they meet all the established inclusion criteria and none of the exclusion criteria, according to the study protocol. Each patient will receive a full explanation of the study objectives and an informed consent form will be signed.

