Once the patient is selected and coded to ensure data protection, after three days of stay, according to the usual protocol, the risk of malnutrition will be studied with CIPA and, later, GLIM will be performed on these patients.

For the evaluation of cell function, the phase angle obtained by bioimpedanciometry (Aker BIA 101 Anniversary) will be used and observing the ratio between reactance/resistance between body cell mass and fat-free mass. Likewise, muscular functionality will be evaluated by dynamometry (using a Jamar dynamometer), taking the maximum value of between two measurements in the dominant arm with an interval of at least one minute between one and the other. In turn, the values under study will be collected and the the data collection notebook according to coding. The risk of sarcopenia will be determined according to values observed in dynamometry and bioimpedance measurement established in the 2019 European consensus on Sarcopenia according to the EWGSOP2 criteria: grip strength determined by dynamometry, positive in males if < 27 kg and in women if < 16 kg, muscle volume, determined by bioimpedance analysis, positive if appendicular skeletal muscle mass < 20 kg in men and < 15 kg in women.

All subjects with a positive test according to the CIPA instrument will be treated according to the usual protocol to correct possible malnutrition or risk thereof,

while subjects with a negative CIPA test but a positive GLIM will be studied and constantly monitored, taking the appropriate measures according to criteria. optional. Patients will be followed up during their hospital stay and 6 months after discharge, prospectively collecting variables for the study of prognostic factors (hospital stay, early readmission rate, mortality).

The study consists of a first cross-sectional part that will be completed once the data of the 490 subjects selected through probabilistic sampling has been collected. The second part of the study will consist of the prospective follow-up of the patients and the variables will be analyzed with prognostic criteria. In these cases, follow-up will end 6 months after discharge. Thus, the total estimated months to complete the study is estimated at 15 months. The study will be conducted entirely at HUNSC.

Difficulties and limitations of the study:

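### The CIPA-versus-GLIM prognosis aim cannot be met as written: the outcome analysis is described only for CIPA-positive patients, and no method allows for both tools classifying the same people.

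*Combined protocol and SAP*

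**What the plan says.** The relevant text is in three places of the combined protocol and SAP.

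- **Secondary endpoints.** One aim is to "Evaluate prognostic variables (mortality, average stay, readmission rate) according to the two tools under study (CIPA vs. GLIM) at discharge", together with early readmissions and six-month mortality. No contrast, hypothesis or effect measure is attached to it.
- **Workplan.** After three days of stay, "the risk of malnutrition will be studied with CIPA and, later, GLIM will be performed on these patients". The cross-sectional part is "completed once the data of the 490 subjects selected through probabilistic sampling has been collected". Follow-up to six months after discharge is described for patients in general.
- **Statistical analysis of the data.** The outcome paragraph opens "For the follow-up study with CIPA positive patients, an initial univariate study of the factors that could determine prognostic levels". Of the univariate step it says "These analyzes will be parametric/non-parametric according to the homoscedasticity and normality of the data in each distribution". Multivariable models follow: "the different models will be compared by the likelihood ratio and the Wald test", and the final model is to be "validated by the Hosmer-Lemeshow calibration test and by the area under the curve (AUC) as a measure of discrimination". The preceding paragraph, on CIPA against GLIM, covers accuracy and agreement only, not outcomes.

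**The concern.** The aim needs outcomes for patients who are positive and negative on each tool. The only outcome analysis described is confined to patients positive on one of them. Followed literally, it can show whether GLIM status matters among CIPA-positives. It cannot show what CIPA status predicts, or what happens to patients whom GLIM finds and CIPA misses.

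If the analysis is widened to everyone followed, a second gap opens. The CIPA-positive and GLIM-positive groups share many patients, and the plan does not say how the tools will then be compared. An analyst could fall into either of two errors:

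- comparing CIPA-positives with GLIM-positives as two independent samples, which misstates the standard error;
- testing CIPA-positive against CIPA-negative, then GLIM-positive against GLIM-negative, and reading a difference between tools from one p-value falling below 0.05 and the other not.

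At stake is whether one listed secondary aim can be answered, and with what precision.

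**Working it through.** **Plan's own figure.** The only design figure is 490 patients, given without a derivation. No expected overlap, kappa for CIPA or outcome rate is stated, so there is nothing to reproduce. The sizes below rest on figures borrowed from elsewhere in the document.

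**Inputs**
- n = 490 (Workplan).
- GLIM-positive share pG = 0.297 (Background, the recent Spanish study using GLIM).
- CIPA-positive share pC = 0.297 or 0.237. The second is the share malnourished or at risk in the older Spanish multicentre study (Background), used as a stand-in.
- Kappa against GLIM of 0.26 and 0.43 (Discussion). These are for other screening tools, not CIPA.

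**Step 1: what the CIPA-positive restriction removes.** CIPA-positives number 490 × 0.297 = 146 or 490 × 0.237 = 116. The restriction therefore leaves out 344 to 374 of 490 patients, and both CIPA-negative cells.

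**Step 2: overlap.** From the definition of kappa, pBoth = pC·pG + kappa × (pC + pG − 2·pC·pG)/2. Expected counts:

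| pC | kappa | CIPA+/GLIM+ | CIPA+/GLIM− | CIPA−/GLIM+ | CIPA−/GLIM− |
|---|---|---|---|---|---|
| 0.297 | 0.26 | 70 | 76 | 76 | 269 |
| 0.297 | 0.43 | 87 | 58 | 58 | 286 |
| 0.237 | 0.26 | 60 | 57 | 86 | 288 |
| 0.237 | 0.43 | 76 | 40 | 70 | 304 |

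(Rows may miss 490 by one through rounding.)

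**Step 3: standard error if the overlap is ignored, common outcome rate**

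Contrast A is the outcome rate in CIPA-positives minus that in GLIM-positives. The ratio of the independent-samples SE to the correct SE is √[V / (V − 2·pBoth/(pC·pG))], with V = 1/pC + 1/pG.
- pC = 0.297: √[6.734/(6.734 − 3.231)] = 1.39 at kappa 0.26; √[6.734/(6.734 − 4.036)] = 1.58 at 0.43.
- pC = 0.237: √[7.586/(7.586 − 3.452)] = 1.35; √[7.586/(7.586 − 4.402)] = 1.54.

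Contrast B is the risk difference by CIPA minus the risk difference by GLIM. The ratio is √[W / (W − C)], with W = 1/[pC(1−pC)] + 1/[pG(1−pG)] and C = 2(pBoth − pC·pG)/[pC(1−pC)·pG(1−pG)]. With equal shares this is 1/√(1 − kappa).
- pC = 0.297: 1/√0.74 = 1.16; 1/√0.57 = 1.32.
- pC = 0.237: √[10.320/(10.320 − 2.708)] = 1.16; √[10.320/(10.320 − 4.478)] = 1.33.

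**Step 4: sensitivity to assumptions**
- The sensitivity and specificity pairs that the Discussion cites for other tools, with pG = 0.297, give A 1.36 to 1.62 and B 1.08 to 1.35.
- Higher assumed overlap, with equal shares of 0.297: A is 1.69 at kappa 0.50 and 2.02 at 0.65; B is 1.41 and 1.69.
- Unequal cell risks: simulated studies of 490 with assumed risks of 20% (both positive), 12% (one positive) and 6% (neither) gave A 1.53 and 1.79, and B 1.20 and 1.39, at kappa 0.26 and 0.43. With no true difference between tools, a nominal 5% unpaired test rejected in at most 0.27% of runs for A and 1.9% for B. The error is conservative.

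**Step 5: comparing two p-values.** Assume sensitivity 65%, specificity 80%, and risks of 20% in CIPA+/GLIM+, 14% in each discordant cell and 10% in CIPA−/GLIM−, so that neither discordant cell carries more risk than the other. Exactly one of the two separate tests reached p < 0.05 in 34% of simulated studies. These risks are invented for illustration. The document gives none.

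**The case against.** The strongest reply is that this is an under-specified aim and not a planned error. Most of that stands.

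- A reader might infer that the plan prescribes independent-groups tests for CIPA against GLIM. It does not. No group test is named, both the parametric and the non-parametric families include paired tests, and independence is only suggested by the homoscedasticity check.
- The multivariable models, likelihood ratio and Wald tests and AUC could hold both tools in one analysis. The plan permits this but does not commit to it.
- The aim can be read as each tool against outcome separately. Positives and negatives on one tool are disjoint, so ordinary tests are valid for that. No sentence says that CIPA-positives will be tested against GLIM-positives or that two p-values will be compared.
- Among CIPA-positives, GLIM-positive against GLIM-negative is a legitimate comparison of separate groups. It would show how patients whom CIPA flags and GLIM does not fare, so the plan is not blind to that group.
- It is also tempting to say that only the discordant cells carry information on which tool predicts better. That is too strong. When the tools flag different numbers of patients, the CIPA-positive versus GLIM-positive difference also depends on the risk in patients positive on both.

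What the reply does not remove is the restriction to CIPA-positive patients. Even the each-tool-separately reading needs CIPA-negative outcomes. The Workplan collects them, but the statistical section does not analyse them.

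**Conclusion.** The point holds in a limited form. The aim, the follow-up and the outcome analysis do not fit together: as written, the statistical section cannot deliver the CIPA-versus-GLIM prognosis comparison, and it states no method that respects the shared patients. That conclusion rests on the text alone.

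The size of the second problem is conditional. If CIPA-positives and GLIM-positives were treated as separate samples, the standard error would be about 1.35 to 1.6 times too large under a common outcome rate and the cited kappas and prevalences. For the difference between risk differences it would be about 1.16 to 1.33 times too large. A single figure such as 1.7 needs an overlap near 65% of positives or unequal cell risks, and the document supplies neither. The kappas belong to other tools in other populations, so the ranges are illustrative. The direction is conservative: intervals too wide and power lost, not false positives. The two-p-value route can mislead in the other direction, but it is a risk and not a stated plan.

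This is a cheap improvement to one secondary aim. The primary accuracy objective and the kappa analysis are unaffected.

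**What to change.** Amend the follow-up paragraph of the statistical analysis section as follows.

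1. Run the prognostic analysis in all followed patients, and reconcile the CIPA-positive wording with the Workplan. An analysis within CIPA-positives can stay as an additional one.
2. Report mortality, stay and readmission in each of the four CIPA by GLIM cells, with 95% confidence intervals.
3. State the tool-versus-tool contrast, and estimate it with a paired or joint method: a patient-level bootstrap of the difference, DeLong's method for the difference in AUC (for death and readmission), or one model containing both tools.
4. State that no tool-versus-tool conclusion will be drawn from independent-sample tests of CIPA-positives against GLIM-positives, or from setting two separate p-values side by side.

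The cost is SAP wording and a little more analysis work, with no new patients or data. The discordant cells will be small, roughly 40 to 86 patients in the scenarios above. At an assumed 12% risk, the 95% half-width is 1.96 × √(0.12 × 0.88/40) = 10 points for 40 patients and 1.96 × √(0.12 × 0.88/86) = 7 points for 86. Cell results should therefore be presented as estimates with wide intervals.

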Adult subjects of both sexes with a hospital stay of more than three days and attached to one of the following departments: general surgery, internal medicine, vascular surgery, digestive system, hematology, nephrology, pulmonology, oncology, neurology, traumatology. The diagnostic evaluation of malnutrition and functionality will be carried out after three days of hospital stay, once the CIPA screening has been carried out.

Exclusion criteria:

Subjects who are not candidates for CIPA nutritional screening at the HUNSC are excluded: with a prognosis of hospital stay of less than or equal to three days; admission to services with a low incidence of malnutrition (ophthalmology, dermatology, obstetrics...); pediatric patient or critical care unit and palliative

care; patients already receiving artificial nutritional treatment. Patients with edemo-ascitic overload will also be excluded.

Written informed consent will be requested from patients who meet all the inclusion criteria and none of the exclusion criteria, and in the case of minors or handicapped, that of their parents or legal guardians will be collected.

Expected criteria for withdrawal of study subjects:

Of all the personal data that is registered, each participant in the study will have access rights for their knowledge, rectification of inaccurate or incomplete data and cancellation (ARCO Rights). Any participant who wishes to exercise their ARCO rights must contact the doctor/investigator responsible at the Study Hospital where said data was collected and submit the corresponding form.

Study variables (primary and secondary):

Variable	Data collection
Sex	Basal
Age	Basal
Weight	Basal
Height	Basal
BMI	Basal
Cause of admission	Basal
Type of admission (urgent)	Basal
Days of hospital stay	Follow-up
Comorbidity	Basal
Diabetes mellitus	Basal
Dinamometry	Basal

Grip strength	Basal
CIPA (variables associated with the performance of the test)	Basal
GLIM (variables associated with the performance of the test)	Basal
Bioimpedanciometry (phase angle)	Basal
Fat Free Mass Index	Basal
Appendiceal skeletal muscle mass index	Basal
Sarcopenia	Basal
Patients with nutritional treatment	Follow-up
Mortality (to six months)	Follow-up
Readmissions (to six months)	Follow-up

Data Collect

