The participation of the patients in the study will consist of performing the screening for malnutrition that is usually used in the hospital (CIPA) to which the GLIM test will be added, considered as the gold standard for this work. The scores of both tests will be recorded together with the data collection through the clinical history or with direct questions to the patient.

For the CIPA test, the BMI, albumin levels and percentage of decreased intake will be taken. For the GLIM test, phenotypic criteria such as non-voluntary weight loss and reduction in muscle mass will also be studied together with etiological criteria to which, in addition to those mentioned for the CIPA test, the presence of inflammation will be added.

Together with the usual work protocols and data depending on the pathology under treatment, the variables collected will be: age, sex, cause of admission, comorbidity, functionality, interventions or treatments per admission, bioimpedance testing, dynamometry, presence of sarcopenia.

Subsequently, the sample of patients with a positive CIPA (as it is currently considered the screening test used in the hospital) will be implemented the therapeutic measures according to the usual protocol, while the subjects with a negative CIPA test but a positive GLIM will be studied. and constant monitoring taking the appropriate measures according to optional criteria. The patients will be followed up for the study of prognostic factors based on the variables obtained.

Statistical analysis of the data:

The data will be recorded in the data recording notebook and imported once the study is closed to specific software for statistical treatment (STATA SE 14; SPSS, V21). The descriptive analysis of the data will divide the variables into qualitative and quantitative. Obtaining means and standard deviations for the quantitative variables and frequencies and proportions for the qualitative data. Graphs will be obtained for a better understanding of the results.

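### The grip-strength comparison by CIPA status would gain, at no data cost, from a sex- and age-adjusted estimate beside the crude kg difference

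*Combined protocol and SAP*

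**What the plan says.** The secondary endpoints under The aims include: "Evaluate whether CIPA positive subjects obtain worse muscle functionality results according to dynamometry than CIPA negative subjects". The population is broad; Inclusion criteria reads "Adult subjects of both sexes with a hospital stay of more than three days", and no upper age limit is given.

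Statistical analysis of the data has three parts that could bear on this aim:

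- The descriptive part: "Obtaining means and standard deviations for the quantitative variables and frequencies and proportions for the qualitative data".
- The cross-sectional part, which opens "For the cross-sectional study of the quality of diagnostic criteria between the CIPA instrument and the current gold standard GLIM" and covers accuracy measures, Youden points, AUC and kappa. It closes by attaching 95% confidence intervals to all point estimates.
- The modelling part, which opens "For the follow-up study with CIPA positive patients, an initial univariate study of the factors that could determine prognostic levels". The univariate tests, the multivariable models and the confounding rule ("The existence of confusion will be evaluated by clinical criteria with a significant change of 10% over the coefficient obtained") all sit here.

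The Workplan fixes the measurement as the higher of two dominant-arm readings in kg. It also gives grip cut-offs, "positive in males if < 27 kg and in women if < 16 kg", as part of the sarcopenia definition. The table of study variables lists sex, age and grip strength at baseline.

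**The concern.** The aim compares two groups that are not randomised and that contain men and women over a wide age range. The only part of the plan that deals with confounding is written for CIPA-positive patients, so it has no CIPA-negative comparator and cannot serve this aim. Followed as written, the plan leads to an unadjusted contrast in kg.

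Two things are then lost. First, a crude difference cannot show whether CIPA-positive patients are weaker than CIPA-negative patients of the same sex and age, which a clinical reader may well want to know. Second, the spread in grip between men and women stays in the error term, so the interval is wider than the collected data require.

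**Working it through.** **The plan's own figures.** No effect size, SD, test or precision target is given for this aim, so there is no figure to reproduce. The total of 490 (Workplan) is taken as given.

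**Which part of the plan serves this aim?** The descriptive part gives group summaries. The cross-sectional part concerns CIPA against GLIM. The modelling part excludes the comparator. The next listed aim relates CIPA to EWGSOP2 sarcopenia and so uses sex-specific cut-offs, but sarcopenia combines grip with muscle mass and does not isolate grip. No adjusted comparison of grip is left.

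**Inputs for the illustration**

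- From the documents: N = 490. The CIPA-positive share is not given. The 29.7% malnutrition prevalence cited in Background is a stand-in: 490 × 0.297 ≈ 146, leaving 344. The other cited prevalence, 23.7%, gives 116 and 374.
- Assumed, not in the documents: sex gap in mean grip 11 kg (8–14), within-sex SD 8 kg (6–10), share of men p = 0.5 (0.4–0.6). The documents' 27 − 16 = 11 kg is a gap between cut-offs, not between means.

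**Precision, with sex unrelated to CIPA status**

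- k = √(1/146 + 1/344) = 0.0988.
- Crude SE = √(SD² + p(1−p) × gap²) × k = √(64 + 0.25 × 121) × 0.0988 = 9.708 × 0.0988 = 0.959 kg.
- Sex-adjusted SE = SD × k = 8 × 0.0988 = 0.790 kg.
- Reduction: 1 − 0.790/0.959 = 17.6%. The 95% CI half-width falls from 1.96 × 0.959 = 1.88 kg to 1.96 × 0.790 = 1.55 kg.
- With 116 and 374 the SEs are 1.032 and 0.850 kg. The percentage is the same because k cancels, so the unknown CIPA-positive share does not affect it.
- Lowest reduction in the assumed range (gap 8, SD 10, p 0.4): 1 − 10/√(100 + 0.24 × 64) = 6.9%.
- Highest (gap 14, SD 6, p 0.5): 1 − 6/√(36 + 0.25 × 196) = 34.9%.

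**Shift, only if the sex mix differs**

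- Shift in crude difference = gap × difference in male share = 11 × 0.10 = 1.1 kg per 10 points (8 × 0.10 = 0.8 to 14 × 0.10 = 1.4).

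**How large a chance imbalance would be**

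- SE of the difference in male share = √(0.5 × 0.5) × 0.0988 = 4.9 points, so 10 points is about 2 SE.
- In kg this is 11 × 0.0494 = 0.543. Since 0.790² + 0.543² = 0.919 = 0.959², the crude SE already contains exactly this chance component. Adjustment removes it.

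**Age.** The documents give no figure relating grip to age, so no size is attached to that part.

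**The case against.** The strongest reply is that the protocol does not ask a same-sex, same-age question. Background speaks of estimating risk "by comparing the prevalence of sarcopenia and the phase angle in patients with positive or negative screening", which is a descriptive contrast for a screening tool. A crude difference in grip answers the parallel question correctly. This stands, and it is why the crude result should be kept.

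It is also fair to say that the scale is not truly absent. The measurement is in kg, quantitative variables are summarised by mean and SD, and the cut-offs belong to the separate sarcopenia aim. Mean kg by CIPA group is the natural reading. The sentence on 95% intervals may cover this aim too, though it closes the diagnostic-accuracy paragraph.

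A reader might go further and infer that the crude test would often produce a false-positive result. The documents do not support that. It would need a real association between CIPA status and sex, which no passage shows, and the CIPA thresholds in Background are the same for men and women. Chance imbalance is already covered by the crude standard error. Power comparisons between possible analyses would likewise rest on an invented effect size.

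What survives is the precision gain, which needs no imbalance, and the absence of any estimate for patients of the same sex and age.

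**Conclusion.** The point holds as a free improvement to one secondary aim, not as an error in the plan. The crude kg difference is valid as description. Without a second estimate, it cannot be separated from any sex or age difference between the groups, and it is less precise than the data allow. Under the assumptions above, adjusting for sex lowers the standard error by about 18% (7–35%). The possible shift of about 1.1 kg per 10-point difference in male share is conditional on an imbalance that may not exist. The case for adjusting for sex leans on the protocol's own sex-specific cut-offs; the case for age is one of principle, with no figure behind it. It would be wrong to infer that the planned comparison is invalid or that the diagnostic-accuracy results are touched: the primary endpoint does not use this analysis.

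**What to change.** In Statistical analysis of the data, add a short paragraph for this aim:

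- Report the crude difference in mean grip (kg), CIPA-positive minus CIPA-negative, with its 95% CI, as the descriptive result.
- Add a linear regression of grip on CIPA status, adjusted for sex and age, and report the CIPA coefficient with its 95% CI as the comparison of patients of the same sex and age.
- Do not adjust for BMI, because it is one of the CIPA items and adjusting would remove part of what is being compared.
- State that the adjusted estimate does not remove other differences between the groups, such as comorbidity or cause of admission.

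The cost is a few sentences of text. Sex, age and grip strength are already collected at baseline, and neither the sample size nor the procedures change.

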The GLIM criteria (Global Leadership Initiative on Malnutrition) aim to provide a consensus at a global level that allows for common criteria for the diagnosis of malnutrition and, in this way, the results obtained through their application can be compared. It is a two-step strategy: first, a validated screening test would be applied to identify malnourished patients or patients at risk of malnutrition and, later, the second step would be carried out, which consists of the diagnostic evaluation of malnutrition and graduation of malnutrition. To evaluate the diagnosis and degree of malnutrition, phenotypic criteria (unintentional weight loss, BMI and reduction in muscle mass) and etiological criteria (decrease in intake and presence of inflammation) are used. A patient would be identified as malnourished when he presents at least 1 phenotypic criterion and 1 etiological criterion. The severity of malnutrition would be assessed using phenotypic criteria [12].

As a result of the publication of these criteria, different studies have been developed that evaluate the sensitivity and specificity of different nutritional screening tools and/or nutritional evolution with respect to GLIM [13]. However, most are not comparable because they are heterogeneous samples and in different areas of medical care.

Another aspect of great interest at the present time is the evaluation of cellular and muscular functionality and its prognostic implications. For the evaluation of cell function, the phase angle has been developed in recent years. It is obtained through the realization of bioimpedance, being the result of the ratio between reactance and resistance. It has been postulated as an indicator of cell integrity and an early marker of malnutrition [14]. On the other hand, muscle functionality can be assessed using dynamometry. It is a simple and accessible technique that

quickly assesses muscle function. In addition, the determination of these parameters (including muscle mass, also given by bioimpedanciometry), would allow us to know the prevalence of sarcopenia that is associated with the appearance of adverse events such as falls, fractures, physical disability and mortality [15].

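### Is GLIM, the reference standard for the primary endpoint, too loosely defined in the plan to be scored?

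*Combined protocol and SAP*

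**What the plan says.** The primary endpoint makes GLIM the gold standard against which CIPA is judged. The Background names the items: "phenotypic criteria (unintentional weight loss, BMI and reduction in muscle mass) and etiological criteria (decrease in intake and presence of inflammation) are used". It adds that malnutrition requires one criterion from each group, and it cites the consensus report.

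The Data Collect section is looser. After listing BMI, albumin and intake for CIPA, it says "For the GLIM test, phenotypic criteria such as non-voluntary weight loss and reduction in muscle mass will also be studied together with etiological criteria", and it completes the thought with "together with etiological criteria to which, in addition to those mentioned for the CIPA test, the presence of inflammation will be added". Its further list reads "the variables collected will be: age, sex, cause of admission, comorbidity, functionality, interventions or treatments per admission, bioimpedance testing, dynamometry, presence of sarcopenia".

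The table of study variables gives GLIM a single baseline row, "GLIM (variables associated with the performance of the test", and CIPA a row of the same form. It separately lists "Fat Free Mass Index" and "Appendiceal skeletal muscle mass index". The only muscle-mass cut-off is in the Workplan, "positive if appendicular skeletal muscle mass < 20 kg in men and < 15 kg in women", and it is given for sarcopenia.

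**The concern.** Sensitivity, specificity, predictive values, likelihood ratios, the diagnostic odds ratio and kappa are all computed against GLIM. CIPA and sarcopenia have printed thresholds; the GLIM items have none. Three matters look open: which muscle measure counts, what counts as inflammation, and whether the phrase about criteria shared with CIPA brings albumin into GLIM.

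Two analysts could then build different 2x2 tables from the same patients, and a choice made after seeing the CIPA results could favour one answer. The Background itself says that the observed prevalence of malnutrition, 10% to 50%, depends partly on the markers used. The albumin reading would also act in one direction. If albumin at CIPA's own threshold counted as an etiological criterion, every patient newly positive on GLIM would already be CIPA-positive, so CIPA's apparent sensitivity and specificity could only rise.

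**Working it through.** **1. Do the two descriptions of GLIM agree?**

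| Background item | Group | Where Data Collect covers it |
|---|---|---|
| Weight loss | phenotypic | added for GLIM |
| BMI | phenotypic | already taken for CIPA |
| Muscle mass | phenotypic | added for GLIM |
| Reduced intake | etiological | already taken for CIPA |
| Inflammation | etiological | added for GLIM |

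Two items come from CIPA and three are added: 2 + 3 = 5, the full Background list. The word for *also* in the Data Collect sentence supports this reading. Intake is the only CIPA item that the Background calls etiological. Albumin is not in its list, which is written as complete.

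**2. Is inflammation missing from the data?** Its lack of a row in the variable table shows little. Albumin, intake and weight loss have no rows of their own either, because each tool's components sit inside one row. The text says inflammation will be added. The section on availability of data and materials says that data collection tools exist.

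**3. Is the muscle item unusable?** Bioimpedance is the only body-composition method described, and both indices are recorded at baseline, so neither option is lost. The choice is not neutral. With assumed heights, the 20 kg sarcopenia cut-off equals 20/1.60² = 7.81 kg/m² or 20/1.80² = 6.17 kg/m². That compares kilograms with an index, however; it does not compare the two listed indices.

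**4. When is GLIM scored?** Under Data Collect and Workplan, GLIM follows CIPA after three days of stay, the result is recorded, and patients who are CIPA-negative but GLIM-positive are monitored. That requires a working classification during the admission. Data are imported for analysis only when the study closes.

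**5. How much could a different choice matter?** The documents give no reclassification rate, so 5% is assumed: 25 of 490 patients move from GLIM-negative to GLIM-positive. Other inputs are the 29.7% GLIM prevalence in the Background and, as stand-ins for CIPA, the MST (56.7%/69.0%) and MUST (64%/82%) accuracies in the Discussion, which itself warns against combining those populations.

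- GLIM-positive: 490 × 0.297 = 146 (rounded); GLIM-negative: 344.
- MST-like table (TP/FP/FN/TN): 83/107/63/237. Sensitivity 83/146 = 56.8%, Wilson 95% interval 48.7% to 64.6%, half-width about 8 points.
- MUST-like table: 93/62/53/282. Sensitivity 93/146 = 63.7%, half-width 1.96 × √(0.637 × 0.363/146) = 7.8 points.
- After the move the denominator is 146 + 25 = 171.

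| The 25 moved patients | MST-like sensitivity | Shift | MUST-like sensitivity | Shift |
|---|---|---|---|---|
| all CIPA-negative | 83/171 = 48.5% | −8.3 | 93/171 = 54.4% | −9.3 |
| split as among GLIM-negatives | 91/171 = 53.2% | −3.6 | 98/171 = 57.3% | −6.4 |
| all CIPA-positive | 108/171 = 63.2% | +6.4 | 118/171 = 69.0% | +5.3 |

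MST-like kappa goes from 0.24 to 0.15, 0.22 and 0.37 in the same order.

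If 80% sensitivity and specificity are assumed instead, the same 5% (24.5 patients, unrounded) takes sensitivity from 80% to 68.5%, 71.4% or 82.9%: shifts of −11.5, −8.6 and +2.9, against a half-width of 6.5.

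**The case for a change.** The strongest reply is that a citation does not record a choice. The consensus is not available here, so whether it fixes each cut-off cannot be checked. Even if it does, the protocol lists two muscle indices and assigns neither to GLIM, and it gives no inflammation rule. A rule that counted any acute illness could classify patients quite differently from a laboratory threshold. Scoring GLIM on the ward does not forbid recoding it later, and the planned 95% intervals would not show that uncertainty.

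Much of this stands. The muscle index and the inflammation rule cannot be read off the documents, and the Data Collect sentence is loosely worded. Three parts do not stand. GLIM is not undefined, because its items and combining rule are stated. Albumin is outside the Background's list, so excluding it would only repeat what is already there. And the choice is not wholly open until analysis, because patients must be classified during their stay. The demand that remains is to write down details of a published standard; it identifies no rule in the plan that gives a wrong result.

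**Conclusion.** No change to the plan follows. This is a gap in detail that analysts can fill sensibly from a published, cited standard and from baseline data that include both muscle indices. The wording that seems to admit albumin is a loose sentence, settled by the Background.

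The conclusion does not rest on the effect being small. Under the assumed 5% reclassification, sensitivity shifts by 3.6 to 6.4 points with a proportional split and by 5.3 to 9.3 at the extremes, using the MST and MUST figures. The proportional shifts lie inside the sampling half-width of about 8 points; the downward extremes slightly exceed it and require every moved patient to share one CIPA status. With 80% accuracy assumed, even the proportional shift (8.6) exceeds its half-width (6.5). None of these sizes comes from the study, and the direction depends on the CIPA status of the patients moved. They show why a report should state the GLIM coding used; they do not show an error in the plan.

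The conclusion assumes that inflammation is captured under the GLIM row, as the text indicates, and that the classification made during admission is the one analysed.
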